3.1 STUDY OUTCOME MEASURES

We aim to detect significant changes in purchase behaviours of ovarian cancer patients prior to diagnosis, and potentially improve the sensitivity of detection of cancer “alert symptoms” by stratifying the analysis on risk profiles, cancer stage or histology.

4. PARTICIPANT ENTRY

4.1 PRE-REGISTRATION EVALUATIONS

No tests need to be done before patient entry to the study.

4.2 INCLUSION CRITERIA

Women, at least 18 years old, recently diagnosed and living with ovarian cancer (all ovarian and peritoneal cancer diagnoses will be eligible), preferably recruited just after diagnosis and during treatment period but are still eligible if diagnosed up to 2 years prior, at the latest, who hold at least one participating high street retailer loyalty card are eligible to join the CLOCS as cases.

Women, at least 18 years old, who have not been diagnosed with ovarian cancer and hold at least one participating high street retailer loyalty card are eligible to join the CLOCS as controls.

4.3 EXCLUSION CRITERIA

Women under the age of 18 years and, since this is a study about ovarian cancer, men will not be eligible to join this study.

4.4 WITHDRAWAL CRITERIA

If at any point, a CLOCS participant wishes to withdraw her participation, she can email the CLOCS research team at [contact] expressing her desire to withdraw consent.

The CLOCS team will then delete that participant’s information from the CLOCS database.

5. PARTICIPANT RECRUITMENT AND CONSENT

The CLOCS will recruit loyalty card holders through advertisement of the study and through clinics around the UK where the CLOCS is open. Advertisement of the CLOCS will start with a press release introducing the study to the general population, inviting loyalty card holders to visit the CLOCS website for more information and possibly participate.

5.1 RECRUITMENT OF WOMEN WITHOUT OVARIAN CANCER (CONTROLS)

Women without ovarian cancer will be recruited through the study website (www.clocsproject.org.uk) where data collection will be safeguarded using an encrypted web form that includes study consent and the self-report questionnaire. No clinical questionnaire is needed for control participants.

The online participation will take up to 15 minutes and data will be transferred immediately to the secure CLOCS server. The website approach was adopted as one of the outcomes of the proof-of-concept study. It aims to provide a transparent environment where potential participants can make informed decisions about participation in CLOCS, and the data risks are minimised using encryption. We have carefully designed the website to inform the general public about how we will process their data in CLOCS, how they can withdraw from the study if they wish to do so and use it as a platform to provide feedback as we progress in the larger CLOCS project. The research team will use several methods to recruit control participants to the study which will include a press release carried out by the project funders and the Imperial College London public engagement team, dissemination of study flyers and leaflets, and social media marketing techniques on Twitter and Facebook using paid advertisement and unpaid methods. The application of the social media recruitment methods will allow researchers to reach a larger cohort in the UK. The application of both paper-based and online recruitment methods will be carried out throughout CLOCS and will be recorded.

5.1.1 ID Verification

In order to adhere with participating high street retailers' policies on data portability, healthy volunteers are required to provide a photo ID in the form of a photo of their passport or drivers licence and a utility bill (e.g. council tax or electricity/gas bill) for ID verification. This is an added step to confirm that participants did not complete the survey on behalf of someone else and to ensure that our research is complaint with the GDPR. Based on this, This information will be stored and deleted as described in section 9.1.6a.

Control participants will be presented with a separate encrypted link for uploading their ID verification details once they consent to the study and complete the survey. If participants do not provide this data, we cannot retain their data or request their information from the retailers. To allow sufficient time to gather the necessary documents and doing it on their own time, we will be sending two reminders to the participants who agreed to the study and have given consent for ID verification. The first reminder will be sent 24 hours after the risk factor questionnaire submission, and a final reminder will be sent one week after the first reminder if the participant still has not completed the ID verification step. The copy of the verification page and the reminders are included in the appendices.

5.2 RECRUITMENT OF WOMEN WITH OVARIAN CANCER (CASES)

Women living with ovarian cancer and at least one loyalty card will be eligible to participate in this study. Ovarian cancer patients will first be approached by a member of their direct care team.

The member of the direct care team will discuss the study with the patients and give them the patient information sheet. They will be made aware that participation is voluntary and even if they do not want to participate it will not affect their care and treatment. They will also be made aware that they can withdraw at any time without affecting their usual care and treatment. Patients will be made aware they can take as much time as they need to decide on participation including discussing their participation with relatives and personal doctors. If they have any further questions that the member of the direct care team cannot answer, they will be encouraged to

contact the CLOCS team using the contact details included in the patient information sheet. The CLOCS team will be available to explain the study further and answer all questions. If they are willing to participate, they will then be given the consent form to sign and complete whenever is convenient for them and return to the study team using the freepost envelope.

5.3. RECRUITMENT CONTINGENCY PLAN (COVID-19 RESTRICTIONS)

5.3.1 During the COVID-19 pandemic, participating recruitment centres are consulting with patients over the phone and not seeing them in person. Where feasible, research nurses or clinicians will recruit patients using the following process:

1. Read through the information sheet and complete the consent form and questionnaires with patient on the phone.
2. Make a copy of the information sheet and completed forms and post them to the patient who chose to take part in CLOCS. This would include a cover letter provided by the CLOCS team.
3. Post the original completed forms to the CLOCS team using the CLOCS Freepost name (Freepost CLOCS PROJECT).

5.3.2 Recruitment for controls will remain on the CLOCS website.

5.4 Any queries from potential participants about joining and participating in the CLOCS will be answered by the research team via the CLOCS email address: [contact].

5.5 Upon choosing to participate, women will complete a consent form to participate in the CLOCS and return it to the study team either via mail or the CLOCS website (controls only), giving permission to the CLOCS team to request access to and analyse loyalty card information from the participating high street retailers.

5.6 The consent form requests permission from the participants for the CLOCS research team to re-contact participants regarding their loyalty card details for verification or future related studies. If a participant consents to be contacted again by the CLOCS team, she will provide either a contact email address or phone number.

5.7 A member of the ovarian cancer patient's clinical team can approach a patient who meets the study eligibility criteria, explain the study to the patient and let the patient know that participation is voluntary, and if the patient does not want to take part, it will not affect patient care.

5.8 Any participant can withdraw from the study at any time after consent without providing any reason.

6. OVARIAN CANCER RISK FACTOR AND SYMPTOM DATA COLLECTION

6.1 Upon choosing to participate in the CLOCS, participants will also complete a questionnaire requesting information about well-established ovarian cancer risk factors and symptoms.

6.1.1 The well-established risk factors include ethnicity, marital status, body mass index, age at menarche, menopausal status, age at menopause, parity,

breastfeeding, hysterectomy, tubal ligation, cancer history, endometriosis, aspirin use, oral contraceptive use, hormone replacement therapy (HRT), family history of ovarian and breast cancers, vaping, and cigarette smoking

- 6.1.2** The questionnaire asks participants about the symptoms experienced (if any) and number of visits to the general practitioner in the year leading up to cancer referral or diagnosis.
- 6.1.3** The questionnaire asks participants about which food and pharmacy stores they shop at regularly, at which stores they own a loyalty card, frequency of use of those loyalty cards, where they heard about the study (for controls only), and the number of people in their household (for adjustment in analysis).
- 6.1.4** In order to understand the impact of COVID-19 on purchase history and ovarian cancer diagnosis delays, the questionnaire includes a question about whether participants have had Covid19 (diagnosed and recovered/diagnosed and still ill/suspected but not formally diagnosed/did not have covid)
- 6.1.5** For participants diagnosed with ovarian cancer (considered cases), this will occur in the clinic or at home if they choose to complete it at home.
- 6.1.6** For participants who do not have ovarian cancer (considered controls), this questionnaire will be completed online.
- 6.2** For participants with ovarian cancer, there will be a separate questionnaire to be completed by their recruiting clinician or member of their healthcare team regarding information about ovarian cancer diagnosis date, type, grade, stage, and surgical outcome, if any. If a patient chooses to complete the questionnaire at home, a member of the clinical care team will send their completed clinical questionnaire with them.
- 6.3** The clinical care teams will not keep a copy of the CLOCS participant consent form.
- 6.4** The member of the clinical care team who recruits the patient in the clinic is responsible for reporting the number of patients recruited to CLOCS on their Local Portfolio Management System (LPMS), and a member of the CLOCS research team will confirm these reports on the Central Portfolio Management System (CPMS).
- 6.5** Once all relevant risk factor and symptom questionnaires are completed, they will be returned to the CLOCS research team either via mail or through the CLOCS website (controls only).
- 6.6** All questionnaire data will be entered into an encrypted database housed on the secure server at Imperial College London, linked only by the pseudonymised study barcode.

7. LOYALTY CARD DATA COLLECTION

- 7.1** The CLOCS team has discussed the study with the two participating high street retailers and data sharing agreements will be signed with them before any data is transferred between the study and the high street retailers.

- 7.2** Women who choose to voluntarily participate in the CLOCS will provide signed, informed consent for their loyalty card data from participating high street retailers to be shared with the CLOCS research team.
- 7.3** When the consent form is returned to the CLOCS research team, the CLOCS team will transfer the encrypted list of CLOCS participants and their loyalty card numbers to a secure Imperial College London file exchange that will be accessible to the high street retailer using a password. The completed paper consent form will be stored in a locked cabinet in a locked room in a building that requires a security badge to access.
- 7.4** The high street retailer will verify the participant information with their loyalty card data and will transfer the encrypted past purchase data back to the CLOCS research team using the secure Imperial College London file exchange.
- 7.5** If the participant's loyalty card details provided by the participant in the consent form does not match the high street retailer's records for that participant's name and the participant consented to be re-contacted, then the CLOCS research team will attempt to contact the participant to verify the card details.
 - 7.5.1** CLOCS participants will only be re-contacted using their preferred method of contact they indicated in the consent form.
 - 7.5.2** The CLOCS team aim to only re-contact participants as needed and will be mindful of participants' time and space.
- 7.6** If the participant's loyalty card details provided by the participant in the consent form do not match the high street retailer's records for that participant's name and the participant did not consent to be re-contacted, then the CLOCS research team will not be able to access the participant's loyalty card data and will exclude them from the study.
- 7.7** The date of recruitment as written on the questionnaire and consent forms will be the final date of purchase data requested by the CLOCS team. At most, up to 6 years of participants' past purchasing data prior to the date of recruitment will be shared with the CLOCS team, depending on the high street retailer's records and when the participant obtained the loyalty card. This includes data about the items purchased (e.g. paracetamol), when (i.e. date of purchase) and where they were purchased (i.e. store postcode). This will not include information on NHS prescriptions or any personally identifiable information, e.g. full name, postcode, ethnicity.
- 7.8** The CLOCS team will save the past purchase data to a secure and encrypted server based at Imperial College London.

8. ASSESSMENT AND FOLLOW-UP

CLOCS participants will only be re-contacted after joining to either confirm loyalty card details and ID verification or to contact participants about future studies related to the CLOCS, subject to their consent to be re-contacted.

The CLOCS is funded from 1 February 2019 to 1 February 2022, but risk factor and symptom data collected in this phase will be available for analysis for up to ten years after completion of the study. Past purchase history data will only be kept for five years or until the

results are published, whichever happens first. Then the purchase data will be completely anonymised and any link to identifiable data deleted.

9. STATISTICS AND DATA ANALYSIS

9.1 Data management and flow

9.1.1 All data will be stored and processed in the College's ISO27001 certified secure environment – the "Secure Enclave". This is a fully managed infrastructure and secure environment providing high availability, resilience and business continuity through multiple servers, back-ups and disaster recovery measures.

A robust data security model has been designed to protect sensitive personal and medical data from the potential risk of unauthorised access or distribution. All information input, viewed or extracted is be protected so that only users with the correct authority and access can create, view, amend or delete information. Access to the system will be governed by authentication and authorisation privileges that will check:

- Access is by an authorised person and the user is who they say they are. This is controlled by a username and complex password;
- The user accessing the system is authorised to do what they are attempting to do. That includes searching, updating, deleting and uploading information at the appropriate authorised level for the database(s) or table(s).

In summary, the security architecture provides the optimal level of protection available through implementing best practice network, hardware, software and data security measures.

9.1.2 All analysis data will be pseudonymised.

9.1.3 Past purchase data will be kept until the results are published or five years from the date of participation in CLOCS, whichever comes first. Then all past purchase data will be anonymised and any link to identifiable data will be deleted.

9.1.4 Ten years after the study is complete, all paper-based documents and electronically held identifiable data, including consent and contact details, will be destroyed or deleted in accordance with Imperial College London's data deletion and retention processes.

9.1.5 The CLOCS research team is committed to protecting the confidentiality of data. Systems have been established for the secure data flow and storage of data to protect confidentiality. All identifiable information, including contact details will remain secure at the research site. A master file, allowing re-identification and linkage will be managed by [name], the CLOCS chief investigator. The access to de-identified data within Imperial College will be limited to approved researchers.

9.1.6 Once completed consent forms, risk factor and symptom questionnaires, and clinical questionnaires (for cases) are returned to the CLOCS research team, all information will be entered onto the secure server. The encrypted list of consenting CLOCS participant names and loyalty card numbers for each

participating high street retailer will be transferred to participating high street retailer 1 (HSR1) and participating high street retailer 2 (HSR2) using a secure file exchange provided by Imperial College London. The file transfer will require a password to access what has been transferred. The flow of data is shown in Appendix 2.

HSR1 and HSR2 will never know the cancer status of participants nor their loyalty card status or details at the other HSR.

- 9.1.6a In accordance with the participating high street retailers' policies, healthy volunteers will need to provide a photo ID and utility bill for ID verification. These will be stored in the Secure Enclave, checked, and confirmed to match the details on the consent form. Once confirmed and the high street retailers have returned the purchase history, the photo ID and utility bill be deleted.
- 9.1.6b After two reminders, if we do not receive relevant information to confirm the identity of the participants, we will remove their consent and questionnaire data from our database and permanently delete their responses as they would be considered 'not validated' and we cannot request their data from HSR1 and HSR2.
- 9.1.7 HSR1 and HSR2 will verify participant loyalty card information, and will transfer encrypted participant past purchase data, linked only via the pseudonymised barcode id, back to the CLOCS research team, in line with the data sharing contracts.
- 9.1.8 The CLOCS research team will then save the encrypted participant purchase history data to the CLOCS secure server to be used for analysis.

9.2 Data analysis

- 9.2.1 The statistical software R will be used for all data analyses.
- 9.2.2 We will define the time prior to diagnosis by which the cases become statistically significantly different in their purchase behaviours to the controls.
- 9.2.3 We will explore this using a multivariable, conditional logistic regression model with ovarian cancer as the outcome and "purchase proportion" at different times prior to diagnosis as the exposure, adjusting for stage and histology and other potentially confounding variables collected from the risk factor questionnaire.
- 9.2.4 We will compare the proportions of purchases in cases to controls, stratified by risk quintiles defined by the epidemiological risk model (estimated n=86 per quintile) or by histology (with expected proportions of high grade serous cases n=335; mucinous cases n=70; endometrioid n=35; clear cell n=35, and low grade serous n=25).
- 9.2.5 We will estimate the predictive values (ROC AUC, PPV, NPV, specificity and sensitivity) of this "early diagnosis" test for each stratum.
- 9.2.6 We will conduct exploratory analyses investigating other methods leveraging the auto correlation in the longitudinal data. Specifically, we will investigate the frequency of purchases and purchase trajectories, to identify purchase patterns (e.g. increasing purchases before diagnosis, purchase peaks, etc.), that are indicative/predictive of the individual disease onset.

- 9.2.7** Using longitudinal approaches, we will investigate if these patterns help in predicting the time-to-onset.
- 9.2.8** This type of approach could be generalised using other purchase categories for further hypothesis generation.

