APPENDIX 3. OVERVIEW OF RESEARCH SITES

21

GLOSSARY OF ABBREVIATIONS

CLOCS	Cancer Loyalty Card Study
HSR1	High Street Retailer 1
HSR2	High Street Retailer 2

KEYWORDS

Ovarian Cancer
Epidemiology
Observational Study
Risk Assessment

STUDY SUMMARY

TITLE Cancer Loyalty Card Study (CLOCS)

DESIGN Observational, retrospective case-control study

AIMS The CLOCS aims to investigate whether or not women have distinctive self-management behaviours prior to seeing their doctor with symptoms that are associated with ovarian cancer.

OUTCOME MEASURES The primary outcome of the CLOCS will be to define the time by which the cases and controls are statistically significantly different in their purchase behaviours leading up to diagnosis on a population level.

The secondary outcome of the CLOCS will be defining a purchase threshold as an “alert” about cancer symptoms in individuals and determining the predictive utility of purchasing behaviours in the early detection of ovarian cancer. Exploratory analyses will include longitudinal analyses, frequency of purchases and an unbiased analysis of other purchase categories.

POPULATION At least 1000 women in the UK (500 ovarian cancer cases and 500 controls)

ELIGIBILITY Women, at least 18 years old, who own at least one participating high street retailer loyalty card are eligible to join the CLOCS. Among these women, those who have been diagnosed with ovarian cancer can join the CLOCS as cases, and those who have no prior ovarian cancer diagnosis are eligible to join as controls.

DURATION 3 years

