1.2 RATIONALE FOR CURRENT STUDY

Approximately 7,400 new cases of ovarian cancer are diagnosed each year in the UK, and with over 4,000 women dying from the disease each year it is a particularly lethal form of cancer. The symptoms are not well known, are vague and non-specific and most women are diagnosed at a late stage when the cancer has already spread around the peritoneum with poor prognosis. Novel methods are needed to improve earlier detection and thereby improve survival from this disease. We hypothesise that a change in purchasing behaviour, primarily an increase in self-medication to treat these vague cancer symptoms, may provide a novel avenue for earlier diagnosis for cancer.

In this study we propose to use loyalty card data from two participating high street retailers (Boots and Tesco) to investigate purchase behaviour as an opportunity for cancer symptom surveillance. We aim to conduct a case-control study of women with ovarian cancer (cases) matched with women who do not have ovarian cancer (controls) and define the time by which the cases are statistically significantly different in their purchase behaviours leading up to date of diagnosis, compared with the control purchase behaviours.

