2. STUDY OBJECTIVES

- 2.1** The primary aim of the CLOCS will be to define the time by which participants with ovarian cancer are statistically significantly different in their purchase behaviours leading up to date of diagnosis, compared with purchase behaviours of participants without ovarian cancer.
- 2.2** The secondary aim of the CLOCS will be to define a purchase threshold as an “alert” about cancer symptoms in individuals and determining the predictive utility of purchasing behaviours in the early detection of ovarian cancer.

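### The primary outcome is the time at which a significance test is passed, with no windows, selection rule, error control or interval, so it measures when a difference is detectable, not when purchasing changes

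*Combined protocol and SAP*

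**What the plan says.** The Study summary (Outcome measures) makes the primary outcome the "time by which the cases and controls are statistically significantly different in their purchase behaviours leading up to diagnosis". Objective 2.1 is to "define the time by which participants with ovarian cancer are statistically significantly different in their purchase behaviours leading up to date of diagnosis", and section 9.2.2 repeats it: "We will define the time prior to diagnosis by which the cases become statistically significantly different in their purchase behaviours to the controls".

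The only method is in 9.2.3: a conditional logistic regression with a purchase proportion "at different times prior to diagnosis as the exposure". Section 3.1, which is headed as the outcome section, adds only this: "We aim to detect significant changes in purchase behaviours of ovarian cancer patients prior to diagnosis".

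The text does not state the number or width of windows, the significance level, which time is reported if several are significant, how error is controlled across times, or an interval for the time. Correlation over time is mentioned only among the exploratory analyses (9.2.6). The contents list gives section 9 only two parts, 9.1 and 9.2, so no other listed section would hold these rules.

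**The concern.** The study's main answer is a lead time, but the plan defines it by a p-value and not by a quantity to be estimated. A significance test is passed where the difference becomes large relative to its standard error. That point moves with the width of the window, with the rule for choosing among times and, if behaviour changes gradually, with the number of women. None of these is a property of when women start to buy differently.

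Two analysts following this plan on the same data could report different lead times, and each would comply. If the windows and rule are chosen after the comparison has been seen, the choice can follow the result. A reader would probably take the reported time as the onset of changed purchasing, which it does not estimate.

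**Working it through.** **Inputs from the plan.** At least 500 cases and 500 controls (section 3). Up to 6 years of purchases counted back from recruitment (7.7), with cases eligible up to 2 years after diagnosis (4.2). For a woman with the full record that leaves at least 6 − 2 = 4 years, or 48 months, before diagnosis. The expected direction is "primarily an increase in self-medication to treat these vague cancer symptoms" (1.2). The plan gives no power, effect or threshold figure to reproduce.

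**Assumed, because the plan gives no value.** Two-sided 5% in each window, with cases above controls. Correlation between months is AR(1) 0 to 0.9 or exchangeable 0.5 to 0.9. Mean z in month t is d(t)·√(n/2), with n per group and no allowance for matching. Wider windows are averages of the same months. Simulations used 20,000 series per setting, and ranges are over the correlations.

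**1. Gradual change, expected crossing.** Let d(t) = 0.30·(13 − t)/12.
- n = 500: 0.30·√250 = 4.74. Then 4.74·(13 − t)/12 > 1.96 gives t < 8.04, so month 8.
- n = 1000: 0.30·√500 = 6.71 gives t < 9.49, so month 9.
- n = 2000: 0.30·√1000 = 9.49 gives t < 10.52, so month 10.

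The curve is the same each time; only n differs.

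**2. Gradual change, simulated.** Median length in months of the unbroken run of significant windows back from diagnosis:

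| Windows | 500 per group | 1000 | 2000 |
|---|---|---|---|
| Monthly | 6-7 | 8-9 | 10 |
| Quarterly | 9 | 9 | 9-12 |
| Half-yearly | 6-12 | | |
| Yearly | 12 | | |

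**3. Abrupt change.** With 0.25 SD in each of months 1 to 12, mean z is 0.25·√250 = 3.95 at n = 500. The monthly median is 12 at both 500 and 1000 per group. At the planned size, therefore, dependence on n needs a gradual change and narrow windows.

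**4. Rounding by the window.** Take an 8-month change with monthly mean z = 3.5. The run goes past the window that contains month 8 in only about 2% of studies at any width. But that window ends at month 9 (quarterly) or 12 (half-yearly, yearly). A time later than month 8 is therefore reported in about 2% of studies (monthly), 68-98% (quarterly), 23-81% (half-yearly) and 69-100% (yearly).

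**5. Earliest significant time instead.** In the same 8-month scenario with 48 monthly windows, the earliest significant month lies before the true change in 9-63% of studies. The 63% is for uncorrelated months. With no true difference, 48 independent tests give at least one significant result with probability 1 − 0.95^48 = 91.5%; with exchangeable correlation 0.9 it is about 19%. A backward run that stops at the first failure keeps the familywise error at 5%, because it can start only if the first window is significant.

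**6. Strata, only if lead times were derived in them.** Section 9.2.4 expects "high grade serous cases n=335; mucinous cases n=70; endometrioid n=35; clear cell n=35, and low grade serous n=25". With the curve of step 1 and equal numbers of controls, month-1 z is 0.30·√(335/2) = 3.88 for 335 cases, which crosses out to month 6. For 25 cases it is 0.30·√(25/2) = 1.06, which never crosses. The effect is the same in both.

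**The case against.** The strongest reply is that the wording already implies a sensible rule. To become different by a certain time, leading up to diagnosis, suggests an unbroken run of significance. Such a run controls error and seldom goes past the window holding the onset. This is the more natural reading and it deserves credit. But the plan does not state it, and the run still moves with window width.

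A second reply is that the study is exploratory: 9.2.3 says the question will be explored. That lowers the stakes, but the Study summary and objective 2.1 still name this time as the primary outcome and aim.

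Four stronger conclusions might be inferred, and the documents do not support them.
- *The lead time always falls short of the true onset.* It does not. An abrupt change is recovered at the planned size (step 3), and wide windows can push the time beyond the onset (step 4).
- *The result is likely to be a false positive.* The largest figures need both the earliest-significant rule and uncorrelated months. Section 9.2.6 itself refers to autocorrelation in these data, so the upper ends are implausible.
- *Lead times will differ spuriously by histology or risk quintile.* Section 9.2.4 compares proportions and 9.2.5 estimates predictive values. Neither says a lead time will be derived by stratum.
- *The individual alert would be unsupported.* Prediction is assessed separately in 9.2.5. The harm here is a misstated lead time.

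That a significance-based time depends on power is also no contradiction in the plan. The error would lie in reporting it as onset.

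**Conclusion.** The concern holds in this form: the primary result is a significance-crossing time whose windows, level, selection rule, error control and interval are all unstated, and it does not estimate when purchasing changes. That conclusion rests on the text alone.

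The sizes rest on the assumed effects, correlations and 5% level. For a gradual change with 500 per group, window width alone moves the median from 6-7 to 12 months. Sample size moves it from 6-7 to 10 months between 500 and 2000 per group with monthly windows, but hardly at all with quarterly windows or an abrupt change. The choice between an unbroken run and the earliest significant month changes the chance of a time before the true change from about 2% to 9-63% with monthly windows. This should be fixed before the comparison is made; it does not invalidate the study.

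**What to change.** Amend 9.2.2-9.2.3 before case and control purchases are compared.

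1. Fix the window grid (width and number) and the reference date that stands in for diagnosis in controls.
2. Make the primary report the adjusted odds ratio for every window, with simultaneous 95% intervals that allow for correlation between windows.
3. If a significance-based time is kept, test backwards from diagnosis at two-sided 5% and stop at the first non-significant window. Report the time only to the resolution of the window. Label it the time by which a difference is detectable at the achieved sample size and chosen windows, not the onset.
4. If strata are compared, compare odds ratios and not these times.

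A change-point estimate of onset is optional.

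**Cost.** SAP wording and some extra analysis, with no new data. Simultaneous intervals are about 34-67% wider than per-window ones: the critical value is roughly 2.6-2.9 for 16 windows and 2.8-3.3 for 48, against 1.96. The backward run is conservative for a gradual change: a median of 6-7 months, with monthly windows and 500 per group, for an effect that reaches zero at month 13.
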